# 3. GLOSSARY

- ASA = American Society of Anesthesiologists
- CRP = C-reactive Protein
  - ERP = Enhanced Recovery Program
- GSD = Glycogen Storage Diseases
- GI = Glycaemic Index
- HbA1c = Glycated haemoglobin
- HPMS = Hydrothermally processed maize starch
- MAL = Maltodextran
- MDT = Multi-disciplinary team
- POD = Post-operative Day
- POMS =
- PONV = Post-operative nausea and vomiting
- POCT = Point of care test
- POAC = Preoperative Assessment Clinic
- PQRS =
- HOMA = Homeostasis Model Assessment
- VAS = Visual Analogue Scale

## 4. Introduction

## 4.1 Background and Rationale

The development of insulin resistance and hyperglycaemia following surgery is a well-documented phenomenon which is associated with increased morbidity and mortality.  Insulin sensitivity is reduced by approximately 50% following elective surgery and persists for at least five days postoperatively in the case of upper abdominal surgery. There is a dose-response relationship between the magnitude of surgery and the degree of insulin resistance postoperatively. In the case of colorectal surgery where the magnitude is variable the change is closely correlated with the duration of surgery. Blood loss is the other independent predictor of the degree of insulin resistance. Therefore this metabolic variable is governed by the degree of surgical trauma itself rather than any predisposing or associated factors.

It appears that endogenous glucose production (EGP) in the liver is unaffected by the suppressive effect of insulin per se, postoperatively. Thus the changes in insulin sensitivity following surgery are secondary to alterations in peripheral glucose uptake alone, and therefore reasonable to assume that the main site for this is skeletal muscle, being the largest organ involved.

The precise mechanism behind this loss of insulin sensitivity is unknown but it has been demonstrated that providing carbohydrates pre-operatively can attenuate this effect. Pre-operative carbohydrate drinks were also found to reduce pre-operative anxiety and hunger. There is also evidence that pre-operative carbohydrate drinks may decrease loss of post-operative muscle mass and function and attenuates protein catabolism. 6,8–11

In addition, receiving a carbohydrate drink 2 hours before the start of anaesthesia does not significantly affect the gastric residual volume compared to patients fasted overnight. 2,4,7,12

This practice, in conjunction with several other interventions, has now become routine with the introduction of Enhanced Recovery Protocols (ERP). These have been shown to reduce length of stay and complication rates for major surgery. A recent ERAS cohort study showed that patients that were treated with preoperative carbohydrates, experienced a 44% reduction in the risk of postoperative symptoms. 

In the search for a treatment for the rare group of inherited, metabolic disorders known as Glycogen Storage Diseases (GSD), a hydrothermally processed maize starch (HPMS) was developed with the aim of providing overnight blood glucose stability with a lower glycaemic index (GI). Two small trials led to the development of a high-amylopectin-containing cornstarch. This compound demonstrated a longer duration of action and a lower initial increase in blood glucose with lower peak concentration compared to standard uncooked cornstarch. 18,19

Hydrothermally processed maize starches, or so-called *Superstarch*, have been used as an alternative to standard, maltodextrin (MAL) based drinks within sports nutrition. They are used to provide stable blood glucose concentrations over time and avoid a spike in insulin concentration, factors which are thought to be advantageous in endurance exercise. This was investigated in a comparison of *SuperStarch* to a standard MAL formulation in a randomized, controlled crossover trial in nine elite cyclists. These participants' ingested 1mg/kg of either MAL or HPMS, rested for 30 minutes, exercised for 150 min at 70% peak VO2 and then at 100% peak VO2 until they fatigued. Following exercise another 1mg/kg of HPMS or MAL was taken and the participants then rested for 90 min. The researchers found that during exercise and recovery HPMS provided more stable blood glucose levels, blunted insulin release and increased levels of fatty acids and glycerol, suggesting increased lipolysis. There was also a reduced initial spike in blood glucose and insulin following ingestion of HPMS compared to MAL (Figures 1 and 4).

Gastric emptying is influenced by carbohydrate load and by osmolality, with increasing osmolality associated with prolongation of gastric emptying. Therefore, it stands that increasing the complexity of the

carbohydrate source would increase speed of gastric emptying whilst providing the same calorific content. Indeed this is the case, with maltodextrin based carbohydrate drinks currently given pre-operatively as part of ERP having little effect on gastric residual volume at the start of anaesthesia, and actually result in less residual volume than a starved state. 4,7,12

[figure not shown]

Fig. 1. Serum glucose response to HMS (closed circles) versus MAL (open circles) before and after cycling bouts (A) and area under the curve analysis for different time ranges (B). Values are expressed as mean  $\pm$  SE. (A) Intervals between time points spanned 15-min periods. a, Fasting blood before first drink ingestion (1 g/kg of body mass); b, onset of cycling bout; c, blood before time to exhaustion; d, blood immediately after time to exhaustion; e, blood 15 min after second drink ingestion (1 g/kg of body mass). (B) Between-trial values were compared using paired-samples t tests. Significant differences between trials ( $P \le 0.05$ ) are italicized. HMS, hydrothermally modified starch; MAL, maltodextrin; PreEx + Ex, before exercise plus exercise.

[figure not shown]

Fig. 4. Serum insulin response to HMS (closed circles) versus MAL (open circles) before and after cycling bouts (A) and area under the curve analysis for different time ranges (B). Values are expressed as mean  $\pm$  SE. (A) Intervals between time points spanned 15-min periods. a, Fasting blood before first drink ingestion (1 g/kg of body mass); b, onset of cycling bout; c, blood before time to exhaustion; d, blood immediately after time to exhaustion; e, blood 15 min after second drink ingestion (1 g/kg of body mass). (B) Between-trial values were compared using paired-samples t tests. Significant differences between trials ( $P \le 0.05$ ) are italicized. HMS, hydrothermally modified starch; MAL, maltodextrin; PreEx + Ex, before exercise plus exercise.

Preload®, the pre-operative carbohydrate drink used in ERP across the NHS and in our institution, has an osmolality of 135mOsm/kg when mixed in the standard dilution (one 50g sachet is diluted with 400ml water). Generation UCAN is a powder-based sports energy drink mix, which makes use of SuperStarch, which has an osmolality of 89mOsm/kg when 60g, is diluted into 500ml water. This indicates that Generation UCAN will be emptied from the stomach more rapidly than Preload®.

The rationale for this pilot study is that HPMS drinks given pre-operatively may result in a further reduction in insulin resistance post-operatively compared with standard maltodextrin containing carbohydrate drinks due to a longer duration of action, a greater reduction in peak glucose concentration, a greater reduction in post-operative blood insulin levels and a greater lipid oxidation. This in turn may lead may lead to a greater reduction muscle loss and morbidity, specifically infectious complications, and in turn time to fitness for hospital discharge.

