#### 5.6 Sample Size

The standard deviation for insulin resistance data was obtained from a previous study of pre-operative carbohydrate treatment in total hip replacement surgery (Soop 2001). Twenty patients in each group are needed based on 80% power for a two-sample t-test, detecting a minimal important difference of 15% in change of insulin resistance on the first postoperative day from baseline, with a standard deviation of 16% and a two-tailed significance level of 0.05. A minimal important difference of 25% was used in a previous study comparing pre-operative carbohydrate treatment with a placebo group for patients who had total hip replacement (Soop 2004) . In this study two carbohydrate drinks are being compared, PreLoad with Generation UCAN. Therefore, a smaller minimal important difference of 15% was deemed appropriate. This sample size calculation allows for 10% attrition.

\*\* Measured twice a day first three postoperative days then alternate days until discharge from hospital.

\*\*\*The baseline HOMA to be done on either of these 2 visits as long as the patient is fasted.

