#### **OPERATIVE DAY PRE-SURGERY**

- Confirm allocated drinks consumed as per instructions & document
- · Thirst and hunger sensation VAS score
- Blood samples on morning of surgery fasted (before consuming the intervention) if not done in POAC.
  - Fasting Glucose
  - Fasting Insulin (3 sample to be taken at 5 minute intervals)
  - Cortisol
  - o CRP
  - HbA1c (if not recently measured)
- Duration surgery (obtained from Theatreman system)
- Volume of blood loss
- Description of operation and type of primary analgesia obtained from Theatreman system or ERP Database
- Calories consumed

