## METHODS FOR ANY ADDITIONAL ANALYSES (EG, SUBGROUP AND ADJUSTED ANALYSES)

If differences are observed in baseline demographic and/or clinical variables prognostic of outcome, then the analysis of the primary and secondary outcomes will be adjusted for using regression-based analysis appropriate to the type of outcome variable. The trial statistician will describe details of sub-group analysis in the statistical analysis plan if possible.

DEFINITION OF ANALYSIS POPULATION RELATING TO PROTOCOL NON-ADHERENCE (E.G., AS RANDOMISED ANALYSIS), AND ANY STATISTICAL METHODS TO HANDLE MISSING DATA (EG, MULTIPLE IMPUTATION) All analysis will be performed according to the intention to treat principle. The primary analysis will be based only on data obtained; sensitivity analysis will explore sensitivity to assumptions around missing data and details will be included in the statistical analysis plan devised by the trial statistician.

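### Duration of surgery and blood loss are named as drivers of the primary outcome and are recorded, but the only adjustment rule covers baseline variables, so precision is lost and chance imbalance in surgical magnitude goes unexamined

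*Protocol*

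**What the plan says.** Protocol section 4.1 describes what determines the primary outcome. On duration it says: "In the case of colorectal surgery where the magnitude is variable the change is closely correlated with the duration of surgery". It names blood loss as the second independent predictor and concludes: "Therefore this metabolic variable is governed by the degree of surgical trauma itself rather than any predisposing or associated factors".

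The operative-day list in section 7.1 collects both items. One entry reads "Duration surgery (obtained from Theatreman system"), and the next is volume of blood loss. The type of operation is recorded as well.

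Section 7.3 compares the change in insulin resistance from baseline to POD 1 with a t-test or a Mann-Whitney test, chosen on skewness, with no covariate. Its paragraph on additional analyses permits regression adjustment of primary and secondary outcomes if differences are observed in "baseline demographic and/or clinical variables prognostic of outcome". No covariate is listed. Section 6.1 states no stratification factor.

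**The concern.** The rationale and the analysis rule point at different variables. Section 4.1 says the outcome follows surgical trauma and plays down patient factors. The adjustment rule in 7.3 is set off by patient factors measured before surgery. Duration and blood loss arise in theatre, so they are not baseline variables in the ordinary sense.

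The statistical analysis plan is not shown and may say more. But section 7.3 defers to it only the sub-group details and the handling of missing data. The class of variable that qualifies for adjustment is written into the protocol itself.

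Two things are at stake in a trial of 40 patients. Variation due to the size of the operation stays in the error term. And if one arm happens to have longer operations, no analysis described in the protocol shows how far that explains the result.

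**Working it through.** **Inputs from protocol section 5.6.** The trial is sized for an unadjusted comparison: "Twenty patients in each group are needed based on 80% power for a two-sample t-test". The target is 15 points between arms in the change to POD 1, the SD is 16 points, alpha is 0.05 two-sided, and the 20 already includes 10% for attrition.

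**Assumption.** The protocol says the correlation is close but gives no coefficient. I take r = 0.3, 0.5 and 0.7 as the multiple correlation of duration and blood loss with the outcome, and r = 0 as the case where adjustment is useless.

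**Step 1: the plan's own figure.** By the normal approximation, n per arm = 2 × (1.96 + 0.84)² × (16/15)² ≈ 17.9, so 18. Allowing for 10% attrition, 18/0.9 = 20. The stated figure reproduces. The exact t calculation needs 19 before attrition.

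**Step 2: unadjusted power at 18 analysed per arm (20 × 0.9).** SE = 16 × √(2/18) = 5.33. The noncentrality is 15/5.33 = 2.81 on 34 degrees of freedom, which gives power of 78%. The 95% CI half-width is 2.03 × 5.33 = 10.8 points.

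**Step 3: adjusted for two covariates.** The residual SD is 16 × √(1 − r²), and 32 degrees of freedom remain. Chance imbalance of the covariates between arms inflates the variance of the treatment effect by (36 − 3)/(36 − 3 − 2) = 33/31 on average. Hence SE = residual SD × √(2/18 × 33/31), and the half-width is 2.04 × SE.

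| r | Residual SD | SE | 15/SE | Power | CI half-width |
|---|---|---|---|---|---|
| unadjusted | 16.0 | 5.33 | 2.81 | 78% | 10.8 |
| 0 | 16.0 | 5.50 | 2.73 | 75% | 11.2 |
| 0.3 | 15.3 | 5.25 | 2.86 | 79% | 10.7 |
| 0.5 | 13.9 | 4.77 | 3.15 | 86% | 9.7 |
| 0.7 | 11.4 | 3.93 | 3.82 | 96% | 8.0 |

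A simulation with two normal covariates and 18 per arm agrees with the adjusted powers to within about half a percentage point. Cutting only the degrees of freedom and leaving out the 33/31 factor would give 82%, 88% and 97% at r = 0.3, 0.5 and 0.7, which is too favourable.

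**Step 4: chance imbalance in duration.** The standardised difference between arms has SE √(2/n): 0.333 at 18 per arm and 0.316 at 20. The chance that it exceeds 0.5 SD in either direction is 2 × (1 − Φ(0.5/SE)) = 13% at 18 and 11% at 20. Taking r as the correlation of duration alone with the outcome, a 0.5 SD imbalance shifts the estimated difference by r × 16 × 0.5 = 2.4, 4.0 or 5.6 points. That is 16%, 27% or 37% of the 15-point target.

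**The case against.** An unadjusted test in a randomised trial is legitimate. It is unbiased, the sample size was calculated for exactly this test, and if 16% is the total SD then variation from surgical trauma is already in it. Ordinary standard errors also cover chance imbalance. All of this stands, so the point concerns efficiency and transparency.

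Keeping duration and blood loss out of the primary model is also defensible. Both arise after randomisation and after the drink is taken. The protocol does not state that the drink leaves them unchanged, surgical technique is at the clinicians' discretion (section 9.3), and only patients are blinded (section 6.2). This stands too, and it is why these two variables belong only in a supportive analysis.

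The powers in the table describe adjustment for duration and blood loss themselves. The documents give no link between planned operation type and insulin resistance, so the gain from that proxy is unknown and would be smaller. The trial also takes only laparoscopic resections under a standardised recovery programme, which may narrow the spread of surgical trauma and lower r.

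What does not stand is the reply that all this is left to the analysis plan. A supportive covariate list could appear there, but it would have to extend a rule that the protocol has already written around baseline variables.

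**Conclusion.** The adjustment rule in section 7.3 is badly matched to the rationale in section 4.1. The consequence is lost precision and an unexamined chance imbalance. Its size depends on an assumed r: about one percentage point of power at 0.3, about 8 at 0.5 and about 18 at 0.7, with a loss of about 3 at r = 0. These figures assume that SD 16% is the total SD in this population and that 18 per arm are analysed.

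A reader might infer more, but the documents do not support it:

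- *That the primary comparison is biased or the sample size wrong.* Randomisation prevents the first, and the stated 20 per group reproduces.
- *That surgical trauma is the largest source of variation.* Section 4.1 speaks of close correlation and of what governs the outcome, but gives no share of variance.
- *That duration and blood loss are barred from every analysis.* The natural reading of 7.3 does not reach them, but a loose reading of clinical variables might, and nothing forbids a supportive model.
- *That the trial is underpowered because the SD comes from hip replacement.* The SD could be larger in colorectal surgery, but the protocol gives no colorectal figure.

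**What to change.** In section 7.3:

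1. Name planned operation type (for example colonic versus rectal resection), fixed before randomisation, as a covariate in the primary model, whatever balance is observed. Neither the t-test nor the Mann-Whitney test takes a covariate, so the primary analysis has to be worded as a regression model.
2. Pre-specify one supportive analysis of the primary outcome that adds duration of surgery and blood loss, reported beside the main result whether or not the arms look balanced. Label both variables as post-randomisation and state the assumption that the drink does not affect them.

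The cost is wording, since the data are known or already collected. Operation type uses one degree of freedom if it has two levels, and duration and blood loss use two more in the supportive model. If the covariates turn out to be unrelated to the outcome, a little power is lost. The supportive model cannot replace the primary result, and the sample size in section 5.6 need not change on this account.

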#### 4.2 OBJECTIVES

The null hypothesis states that there is no difference in post-operative insulin resistance between patients who drink *Preload*® compared to those drinking *Generation UCAN* preoperatively.

## 4.3 TRIAL DESIGN

3

Randomised controlled single-blinded (subject only) parallel group, 1:1 allocation ratio superiority framework study.

## 5. Methods: Participants, interventions, and outcomes

#### 5.1 STUDY SETTING

Royal Blackburn Hospital, a large district general hospital, and Royal Surrey County Hospital NHS Foundation Trust, a university hospital, which both perform high volumes of major abdominal surgery with well established Enhanced Recovery Programmes.

#### 5.2 ELIGIBILITY CRITERIA

#### **INCLUSION CRITERIA**

- Patients > 18 years of age
- Laparoscopic colorectal resection
- Included in Enhanced Recovery Protocol
- ASA 1-3
- Able to give consent

#### **EXCLUSION CRITERIA**

- Non-English speaker
- Pregnancy
- Diagnosed diabetes mellitus (diet, drug or insulin controlled)
- Diagnosed impaired glucose tolerance (fasting glucose in POAC >5.5 mmol/l and/or HbA1C>5.7%)
- Decreased gastrointestinal motility (from medication or disease) or predisposition to reflux
- Diagnosis of Inflammatory Bowel Disease
- Allergy to either preoperative carbohydrate drink

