# 5.3 Interventions

Following consent and randomisation at the Preoperative Assessment Clinic (POAC) visit one group will receive the current pre-operative carbohydrate solution, *Preload*® (a maltodextrin solution), and the other group will receive *Generation UCAN* (a hydrothermally modified starch solution) to take home.

In both cases these will be dispensed as a powder in a clear plastic zip lock bag to ensure blinding of the patient (the research team will have decanted the appropriate dose of each supplement into these bags and will be aware of the allocated intervention). This will be a single sachet, in the case of *Preload®*, and an equivalent weighed and measured volume from a large tub, in the case of Generation UCAN. Both groups will be instructed to reconstitute the powder provided in 400mls of water on the day of surgery, and consume it between two and three hours before surgery, as per standard practice in the ERP.

Both groups will also be instructed to consume approximately 500mls (1 pint) of water with their evening meal the evening before surgery to remain well hydrated.

The Control group will receive 47.5g of carbohydrate in the form of Preload®.

The Intervention group will receive 56.55g of flavoured Generation UCAN (providing 47.5g of carbohydrate).

All other aspects of patient care will be standardized as per our ERP (see Appendices).

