# 5.5 Participant timeline

	Enrolment	Allocation	Close-out					
TIMEPOINT	Surgical OPD	POAC	Op Day	POD1 & POD2	POD3	POD5	POD7	D/C Hospital
ENROLMENT:								
Eligibility screen	Х							
HbA1C*			Х					
Informed consent		Х						

PQRS score	Х	Х		Х		Х	
Fasting glucose (POCT)	X*						
Allocation	Х						
INTERVENTIONS:							
Preload®		Х					
Generation UCAN		Х					
ASSESSMENTS:							
Baseline Data Collection	Х						
Outcome Data Collection		Х	Х	Х	Х		х
Gastric Volume Measurement		Х					
Blood samples		Х	Х	Х			
Insulin Resistance (HOMA) Calculation	X**	X**	Х	Х			
Hand Grip Strength**	х		х	Х	Х	Х	

\*If a patient has a recent HbA1c result available on the laboratory results system this will be used for screening as opposed to point of care blood glucose.

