## 9.3 Consent

Once the research team are informed about an eligible patient as described in the recruitment section they will meet them at their next hospital attendance & provide them with a written Patient Information Sheet (PIS) and a verbal description of the study along with contact numbers should they wish further information or clarification. They will be followed by telephone in the interim to gauge interest, and again at their preoperative assessment clinical visit to ascertain if they wish to participate. Some patients may be encountered for the first time at this clinic and may be willing to participate after sufficient time to absorb the PIS, which will vary individually. If so, consent will be taken followed by randomisation in order to provide them with their allocated bags of *PreLoad®* or *Generation UCAN* to take home with them to take as directed in the intervention section.

No other aspect of care will be altered apart from that detailed in the study protocol (i.e. provision of different pre-operative drink in intervention arm). The conduct of anaesthesia and planned surgical technique will be at the discretion of the responsible clinicians.

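### For patients without a recent HbA1c, the HbA1c exclusion may be known only after randomisation, and the protocol disagrees with itself on which glycaemic test decides eligibility

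*Protocol*

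**What the plan says.** - **Criterion.** Section 5.2 (exclusion criteria) lists "Diagnosed impaired glucose tolerance (fasting glucose in POAC >5.5 mmol/l and/or HbA1C>5.7" per cent. Either test is enough to exclude.
- **Time of allocation.** Section 5.3 gives out the drinks "Following consent and randomisation at the Preoperative Assessment Clinic (POAC) visit". Section 9.3 gives the same order: "consent will be taken followed by randomisation in order to provide them with their allocated bags".
- **Screening at POAC.** The first item of the POAC list in section 7.1 is a fasting point-of-care glucose, whose stated purpose is to confirm eligibility; a previous HbA1c may be used in its place. The footnote to the timeline in section 5.5 says of a recent HbA1c that "this will be used for screening as opposed to point of care blood glucose".
- **HbA1c when none is recent.** Section 7.1 lists it among the POAC baseline bloods and again on the operative day: "Blood samples on morning of surgery fasted (before consuming the intervention) if not done in POAC", including "HbA1c (if not recently measured").
- **Fasting at POAC.** A timeline footnote says "The baseline HOMA to be done on either of these 2 visits as long as the patient is fasted", the two visits being POAC and the operative day. Section 9.3 adds that "Some patients may be encountered for the first time at this clinic".
- **Late ineligibility.** Under the withdrawal rules in section 9.3, a randomised patient later found ineligible is withdrawn, withdrawn patients are not replaced, and data collected before withdrawal are kept. Section 7.3 applies intention to treat to all analyses and bases the primary analysis on the data obtained.

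**The concern.** An exclusion criterion should be settled before allocation. Here one limb of a two-limb criterion can be settled afterwards, and the sections differ on whether that limb adds to the other or replaces it.

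The criterion bears directly on the primary outcome. HOMA is computed from fasting glucose and insulin, so whether patients with raised glycaemic markers are in the trial affects both the level and the spread of what is measured. A patient found ineligible after allocation either stays, contrary to 5.2, or leaves under 9.3. If that patient leaves before the sample on postoperative day 1 (POD 1), a randomised patient has no primary outcome, in a trial of 40 that does not replace withdrawals. The two centres could also read the rule differently and enrol different populations.

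**Working it through.** **Applying the rules to each kind of patient**

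1. *Recent HbA1c on file, above the limit.* Excluded before allocation. No problem.
2. *No recent HbA1c, fasted point-of-care glucose above 5.5 mmol/l.* Excluded at POAC. No problem, provided the result is read before allocation. Section 7.1 implies this but does not state it.
3. *No recent HbA1c, fasted glucose within the limit.* Passes the POAC check and is randomised. HbA1c is drawn at POAC or on the morning of surgery. If it exceeds 5.7%, section 5.2 excludes the patient after allocation. With an operative-day sample this is certain, because the patient already holds the drink. With a POAC sample it is likely but inferred: the blood-sampling appendix sends HbA1c to laboratory HPLC analysers and gives no turnaround time.
4. *Recent HbA1c within the limit, fasting glucose from the POAC baseline bloods above 5.5 mmol/l.* Eligible under 5.5 and 7.1, where HbA1c takes the place of glucose. Excluded under 5.2, where either test suffices. This contradiction does not depend on timing.
5. *No recent HbA1c, not fasted at POAC.* The protocol gives no rule.

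In the extracted timeline table the HbA1c row is marked under the operative day. The table is broken, so I give that no weight; the operative-day list in 7.1 establishes the point alone.

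**What the sample size can absorb**

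Inputs from section 5.6: difference 15%, SD 16%, two-sided alpha 0.05, power 80%, attrition 10%, 20 per group.

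- Normal approximation: n = 2 × (1.960 + 0.842)² × (16/15)² = 17.9, so 18 per group, and 18/0.9 = 20. The stated figure is reproduced.
- The exact t-test gives 18.87, so 19 per group, and 19/0.9 = 21.1, so 22.
- Attrition allowance: 40 − 36 = 4 patients.

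Let f be the share lost to late HbA1c exclusion before POD 1, on top of the 10%. Evaluable patients per group are 20 × 0.9 × (1 − f). The documents do not give f; the values below are assumptions that show scale only.

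| f (assumed) | Evaluable per group | Power, normal | Power, t-test |
|---|---|---|---|
| 0% | 18.0 | 80% | 78% |
| 5% | 17.1 | 78% | 76% |
| 10% | 16.2 | 76% | 73% |
| 20% | 14.4 | 71% | 68% |
| 30% | 12.6 | 65% | 62% |

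**The case against.** The strongest reply is that the protocol already screens before allocation. The POAC list opens with a point-of-care glucose to confirm eligibility, or an existing HbA1c, and either can be read at that visit. The later HbA1c is listed beside baseline insulin, cortisol and CRP and is not labelled an eligibility test. On this reading it only describes baseline and nobody is excluded late.

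Much of this stands. A reader might infer that the whole glycaemic exclusion can be tested only after randomisation. The documents do not support that: the glucose limb and an existing HbA1c can both precede allocation. A reader might also infer that an unfasted patient without an HbA1c is randomised anyway. No section says so. The fasting footnote concerns baseline HOMA, and the remark about patients first met at POAC concerns consent. On such patients the protocol is silent.

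What the reply does not remove is the wording of 5.2. It makes HbA1c a ground for exclusion in its own right and does not restrict this to results available at screening. A site that follows 5.2 must act on a late result above the limit, and 9.3 then requires withdrawal. If the baseline-only reading is intended, the protocol has to say so.

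It is also fair that no mechanism makes late exclusion differ by arm: the operative-day sample is taken before the drink. Differential bias is therefore not shown; the demonstrable costs are lost patients and an unclear trial population.

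**Conclusion.** The concern holds in two limited parts. First, for patients with no recent HbA1c and an acceptable POAC glucose, the HbA1c limb may be known only after randomisation. Those above the limit then meet an exclusion criterion and are withdrawn without replacement. This conflicts in effect with intention to treat where withdrawal precedes the POD 1 sample, because the retained earlier data do not include the primary outcome. Second, section 5.2 contradicts sections 5.5 and 7.1 on whether either test excludes or a recent HbA1c stands in for glucose; what counts as recent is not defined.

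The size is unknown. The protocol gives neither the proportion without a recent HbA1c nor the proportion of those who would exceed 5.7% after passing the glucose check. The power figures above depend on the assumed loss, and on every such patient leaving before POD 1. They show only that a design with 4 patients of slack has little room for avoidable withdrawals. The contradiction itself needs no assumption, and an analysis plan cannot repair it, because it governs who is enrolled.

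**What to change.** Reconcile sections 5.2, 5.5 and 7.1 (both the POAC and the operative-day lists) to one rule:

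- State which test decides eligibility: either test excludes, or a recent HbA1c replaces glucose. Use the same wording throughout.
- Require the deciding result before randomisation: an existing HbA1c within a stated look-back, or a point-of-care glucose confirmed as fasted.
- If neither is available at POAC, take consent and bloods there, and defer randomisation and dispensing until the result is known.
- State that an HbA1c drawn at or after randomisation describes baseline only and does not trigger withdrawal under 9.3.

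The cost is a protocol amendment and a revised timeline table. No test is added. Some patients will have to collect the drink after the POAC visit; how many depends on how often neither result is available there, which the sites can find out.
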